## 6.2. Exclusion Criteria

Patients/subjects will be excluded from study enrollment if they meet any of the following criteria at screening and/or enrollment:

### 6.2.1. For Healthy Subjects and Patients with Psoriasis

- [16] are investigative site personnel directly affiliated with this study and their immediate families. Immediate family is defined as a spouse, biological or legal guardian, child, or sibling.
- [17] are Lilly employees or are employees of a third-party organization involved with the study.
- [18] are currently enrolled in a clinical study involving an IP or any other type of medical research judged not to be scientifically or medically compatible with this study or have received any non-biologic IP within 30 days or 5 half-lives (whichever is longer) of their initial screening visit.
- [19] have previously completed a clinical trial investigating CCI (IL-23 antibody) or CCI (CGRP antibody) and have previously received either of these IPs.

- [20] a marked baseline prolongation of QT/corrected QT interval (QTc) (for example, repeated demonstration of a QTcB interval >470 ms);
  - A history of additional risk factors for Torsades de Pointes (for example, heart failure, persistent hypokalemia, family history of long QT syndrome);
  - The use of concomitant medications that prolong the QT/QTc interval.
- [21] have known or ongoing neuropsychiatric disorders.
- [22] for Parts B and C only, patients who have answered ‘yes’ to either Question 4 (Active Suicidal Ideation with Some Intent to Act, Without Specific Plan) or Question 5 (Active Suicidal Ideation with Specific Plan and Intent) on the “Suicidal Ideation” portion of the Columbia-Suicide Severity Rating Scale (C-SSRS), or answer “yes” to any of the suicide-related behaviors (actual attempt, interrupted attempt, aborted attempt, reparatory act or behavior) on the “Suicidal Behavior” portion of the C-SSRS; and the ideation or behavior occurred within the past month.

NOTE: a patient does not necessarily have to be excluded if they have self-injurious behavior that would be classified as non-suicidal self-injurious behavior. Of course, if this situation arises, it is likely the subject should be referred to a psychiatrist or appropriately trained professional.
- [23] have evidence of clinically significant active infection, fever of 100.5°F (38°C) or above, at screening or baseline (Day 1).
- [24] had any surgical procedure (except for minor surgery requiring local or no anesthesia and without any complications or sequelae) within 12 weeks prior to screening, or any planned surgical procedure scheduled to occur during the study.
- [25] have received live vaccine(s) (including attenuated live vaccines) within 28 days of screening or intend to receive during the study (non-live or inactivated vaccinations are allowed).
- [26] have a history of multiple or severe allergies or has had an anaphylactic reaction to prescription or non-prescription drugs or food.
- [27] have a history of allergy to mAbs or to the drug excipients, or have clinically significant multiple or severe drug allergies, intolerance to topical corticosteroids, or a history of severe post-treatment hypersensitivity reactions (including, but not limited to, erythema multiforme major, linear immunoglobulin A [IgA] dermatosis, toxic epidermal necrolysis, or exfoliative dermatitis).
- [28] have had serious, opportunistic, or chronic/recurring infection within 6 months prior to screening. Examples include but are not limited to infections requiring IV antibiotics, hospitalization, or prolonged anti-infective treatment.

- [29] had any malignancy within the past 5 years except for basal cell or squamous epithelial carcinomas of the skin that have been resected with no subsequent evidence of recurrence for at least 3 years prior to screening and cervical carcinoma in situ with no evidence of recurrence within the 5 years prior to baseline.
- [30] current smoker >10 cigarettes or other tobacco products per day. Are unable/unwilling to stop smoking tobacco products while in the study unit. Heavy smokers (as per judgment of the investigator) should be excluded from the study.
- [31] are regular users of known drugs of abuse and/or have positive findings on urinary drug tests at screening; OR an average weekly alcohol intake that exceeds 21 units per week (males) or 14 units per week (females), OR are unwilling to stop alcohol consumption during study visits/time in the research unit (1 unit of alcohol = 12 oz or 360 mL of beer; 5 oz or 150 mL of wine; 1.5 oz or 45 mL of distilled spirits).
- [32] have donated blood of more than 500 mL within the previous 30 days of study screening.
- [33] show evidence of active or latent tuberculosis (TB), as documented through medical history and examination, chest x-rays (posterior, anterior, and lateral) for patients with psoriasis only (Part C), and TB testing: either a positive tuberculin skin test (TST; defined as a skin induration >5 mm at 48 to 72 hours, regardless of *Bacillus Calmette–Guérin* or other vaccination history) or a positive (not indeterminate) QuantiFERON®-TB Gold test. The choice to perform a TST or a QuantiFERON-TB Gold test will be made by the investigator according to local licensing and standard of care. The QuantiFERON-TB Gold test can only be used in countries where it is licensed, and the use of this test is dependent on previous treatment(s). This test may not be suitable if previous treatment(s) produce significant immunosuppression.
- [34] have known hypogammaglobulinemia or a screening serum IgG <565 mg/dL, IgM <40 mg/dL, or IgA <70 mg/dL.
- [35] are immunocompromised.
- [36] have presence of significant uncontrolled cerebro-cardiovascular (for example, myocardial infarction, unstable angina, hypertension, moderate to severe [New York Heart Association Class III/IV] heart failure, or cerebrovascular accident), respiratory, hepatic, renal, gastrointestinal, endocrine, hematologic, neurologic or neuropsychiatric disorders or abnormal laboratory values at screening that, in the opinion of the investigator, pose an unacceptable risk to the subject if participating in the study or of interfering with the interpretation of data.
- [37] in the opinion of the investigator or sponsor, are unsuitable for inclusion in the study.

### ***6.2.2. For Healthy Subjects Only***

- [38] intend to use herbal, over-the-counter, or prescription medication within 14 days prior to dosing and during the study, other than estrogen/progesterone as a form of hormone replacement therapy. Subjects taking these medications should be on stable doses for at least 28 days prior to screening. Certain medications, for example vitamin supplements and local anesthetics, may be permitted at the discretion of the investigator.
- [39] have received Ig-based biologic therapies (such as mAbs, including marketed or investigational biologic therapy) within the past 6 months, or at any time received the compounds specified in criterion #19.
- [40] have an abnormal blood pressure, pulse rate, and/or temperature as determined to be clinically significant by the investigator.
- [41] have evidence of chronic viral infection:
  - [41a] show evidence of hepatitis C and/or positive hepatitis C antibody with confirmed presence of hepatitis C virus (HCV) ribonucleic acid (RNA) at screening.
  - [41b] show evidence of hepatitis B and/or positive hepatitis B surface antigen or are positive for hepatitis B core antibody (HBcAb) and negative for hepatitis B surface antibody (HBsAb) at screening.
  - [41c] show evidence of human immunodeficiency virus (HIV) infection and/or positive for HIV antibodies at screening.
  - [41d] have had symptomatic herpes zoster within 3 months (for patients in Part C) or 6 months (for healthy subjects in Parts A and B) prior to screening that constitutes (per investigator's judgment) a risk to the subject when taking the study medication or that may interfere with the interpretation of study data.
- [42] are not willing to receive multiple subcutaneous injections.

Patients with a previous diagnosis of hepatitis C who have been treated with antiviral therapy and achieved a sustained virological response may be eligible for inclusion in the study, provided they have no detectable HCV RNA on the screening test for this protocol. A sustained virological response is defined as an undetectable HCV RNA 12 weeks after completion of a full, documented course of an approved antiviral therapy for HCV.

Patients who have spontaneously cleared HCV infection, defined as:

- (i) a positive HCV antibody test and

(ii) a negative HCV RNA test, with no history of anti-HCV treatment, may be eligible for inclusion in the study, provided they have no detectable HCV RNA on screening for this study.

Based on the judgment of the investigator, any patient exhibiting behaviors that would put them at risk for re-infection with HCV may be discontinued from the study.

Any patient with a history of HCV infection who develops elevated ALT  $>3\times$  ULN during the study will be tested for HCV RNA in addition to a full liver evaluation as described in Section 9.4.4.1.

Anyone diagnosed with hepatitis C during the study will be discontinued from the study and should receive appropriate follow-up medical care.

- [49b] show evidence of hepatitis B and/or positive hepatitis B surface antigen or are positive for HBcAb and negative for HBsAb at screening.
- [49c] show evidence of HIV infection and/or positive for HIV antibodies at screening.
- [49d] have had symptomatic herpes zoster within 3 months (for patients in Part C) or 6 months (for healthy subjects in Parts A and B) prior to screening that constitutes (per investigator's judgment) a risk to the subject when taking the study medication or that may interfere with the interpretation of study data.
- [50] are unable or unwilling to avoid excessive sun exposure or use of tanning booths for at least 4 weeks prior to baseline and during the study.

### **6.3. Lifestyle and/or Dietary Requirements**

Throughout the study, patients/subjects may undergo medical assessments and review of compliance with requirements before continuing in the study.

#### **6.3.1. Meals and Dietary Restrictions**

Subjects should not eat after midnight during the night before study drug administration. Water is permitted. Subjects may eat breakfast approximately 2 hours postdose. A normal diet may be consumed at all other times during the study.

#### **6.3.2. Caffeine, Alcohol, and Tobacco**

##### **6.3.2.1. Caffeine**

Subjects and patients should not consume caffeine from the start of each dosing day to 12 hours postdose. Consumption of non-caffeinated beverages is permitted at any time during the study.

##### **6.3.2.2. Alcohol**

Subjects should not consume alcohol for at least 24 hours prior to dosing. During outpatient periods, all subjects should be advised to limit alcohol consumption to no more than 2 units per day.

### 6.3.2.3. Smoking

Subjects should be willing and able to abide by smoking restrictions at the study sites during both the in-house period and outpatient visits.

### 6.3.3. Activity

Subjects should avoid strenuous exercise and/or activity for at least 48 hours prior to dosing and scheduled visits.

### 6.3.4. Contraception

Women of childbearing potential (WOCBP) are excluded from Parts A and B of the study. For Part C, WOCBP who are abstinent (if this is complete abstinence, as their preferred and usual lifestyle) or in a same sex relationship (as part of their preferred and usual lifestyle) must agree to either remain abstinent or stay in a same sex relationship without sexual relationships with males. Otherwise, WOCBP must use 2 effective methods of contraception for the entirety of the study. Abstinence or contraception must continue following completion of study drug administration for 5 half-lives or until plasma concentrations are equal to or below the pharmacologic effect level, whichever is longer.

- The WOCBP must test negative for pregnancy prior to initiation of treatment as indicated by a negative urine pregnancy test at the screening visit followed by a negative serum pregnancy test within 24 hours prior to exposure to LY3316531 or placebo.
- Two effective methods of contraception (such as male or female condoms with spermicide, diaphragms with spermicide or cervical sponges) will be used. The subject may choose to use a double-barrier method of contraception. Barrier protection methods without concomitant use of a spermicide are not a reliable or acceptable method. Thus, each barrier method must include use of a spermicide (that is, condom with spermicide, diaphragm with spermicide, female condom with spermicide). It should be noted that the use of male and female condoms as a double-barrier method is not considered acceptable due to the high failure rate when these methods are combined.
  - Of note, 1 of the 2 methods of contraception may be a highly effective (less than 1% failure rate) method of contraception (such as combination oral contraceptives, implanted contraceptives, or intrauterine devices).

Women not of childbearing potential may participate and include those who are

- infertile due to surgical sterilization (hysterectomy, bilateral oophorectomy, or tubal ligation), congenital anomaly such as mullerian agenesis; or
- postmenopausal – defined as either
  - a woman at least 50 years of age with an intact uterus, not on hormone therapy, who has had either
    - cessation of menses for at least 1 year, or

- at least 6 months of spontaneous amenorrhea with a follicle-stimulating hormone >40 mIU/mL; or
- A woman 55 years of age or older not on hormone therapy, who has had at least 6 months of spontaneous amenorrhea; or
- A woman at least 55 years of age with a diagnosis of menopause prior to starting hormone replacement therapy.

Men, regardless of their fertility status, with non-pregnant WOCBP partners must agree to either remain abstinent (if this is their preferred and usual lifestyle) or use condoms as well as 1 additional highly effective (less than 1% failure rate) method of contraception (such as combination oral contraceptives, implanted contraceptives, or intrauterine devices) or effective method of contraception (such as diaphragms with spermicide or cervical sponges) for the duration of the study and until their plasma concentrations are below the level that could result in a relevant potential exposure to a possible fetus, predicted to be 5 months following the last dose of study drug.

- Men and their partners may choose to use a double-barrier method of contraception. (Barrier protection methods without concomitant use of a spermicide are not an effective or acceptable method of contraception. Thus, each barrier method must include use of a spermicide. It should be noted, however, that the use of male and female condoms as a double-barrier method is not considered acceptable due to the high failure rate when these barrier methods are combined).
- Men with pregnant partners should use condoms during intercourse for the duration of the study and until the end of estimated relevant potential exposure in WOCBP (5 months following the last dose of study drug).
- Men should refrain from sperm donation for the duration of the study and until their plasma concentrations are below the level that could result in a relevant potential exposure to a possible fetus, predicted to be 5 months following the last dose of study drug.
- Men who are in exclusively same sex relationships (as their preferred and usual lifestyle) are not required to use contraception.

#### 6.4. Screen Failures

Healthy subjects who do not meet the criteria for participation in this study (screen failure) may not be re-screened; however, re-assessment of laboratory parameters will be allowed once if handling issues, damaged samples, or hemolyzed samples may have confounded the measurement results.

Any patient with psoriasis who has a screening laboratory assessment that falls outside of the protocol-specified inclusion/exclusion parameters may (based on investigator judgment) undergo repeat laboratory testing 1 time without being considered a screen failure (this does not include TB testing).

In addition, participants who were eligible for inclusion in previous cohorts, but were not randomized for nonmedical reasons, may be reassessed, following a discussion with the sponsor.

If rescreening is performed, the individual must sign a new informed consent form (ICF) each time and will be assigned a new identification number.

## 7. Treatment

### 7.1. Treatment Administered

The drug product LY3316531 is supplied for clinical trial use as solution formulation in glass vials. Further dilution may be needed for SC and IV administration. See Pharmacy Instructions for more information.

Placebo will be sterile saline (0.9% NaCl). Placebo doses should be held in the pharmacy for an equivalent amount of time as is required to prepare doses of LY3316531.

The IP or placebo will be administered as SC injection(s) or a slow IV infusion over at least 30 minutes. Sites must have resuscitation equipment, emergency drugs, and appropriately trained staff available during the infusion and for at least 6 hours after subjects have completed receiving their infusion.

Injection site selected for SC administration should be the abdominal region approximately 5 cm from the umbilicus and the treatment is administered through the needle applied at approximately 45° with pinching of the skin. Because subjects may receive multiple injections per dose, each injection should be administered in a different abdominal quadrant (right upper quadrant, left upper quadrant, right lower quadrant, or left lower quadrant) and the quadrant used should be recorded at the time of the injection. Subcutaneous administration of LY3316531 should be done by a limited number of individuals for consistency. The same type of syringe and needle (CC1 [REDACTED]) should be used for all subjects to ensure all injections are delivered to a consistent depth target into the SC space.

All clinical trial materials provided to the investigator will be stored in a secure place, assigned using the interactive web response system, and dispensed by appropriately trained persons. The dispensing of the IPs will be fully documented. Detailed records of the amounts of the IP received, dispensed, and remaining at the end of the study will be maintained.

The investigator or designee is responsible for

- explaining the correct use of the IP(s) to the site personnel
- verifying that instructions are followed properly
- maintaining accurate records of IP dispensing and collection, and
- returning all unused medications to Lilly or its designee at the end of the study.

**Note:** In some cases, sites may destroy the material if, during the investigative site selection, the evaluator has verified and documented that the site has appropriate facilities and written procedures to dispose of clinical materials.

#### 7.1.1. Packaging and Labeling

LY3316531 will be supplied to the investigative sites by Lilly. Clinical trial materials will be labeled according to the country's regulatory requirements. All IPs will be stored, inventoried,

reconciled, and destroyed according to applicable regulations. Clinical trial materials are manufactured in accordance with current good manufacturing practices.

LY3316531 is supplied for clinical trial use as solution in vial with study-specific labels. The 2-mL vial is manufactured to contain 150 mg of LY3316531 (75 mg/mL). Vials will be supplied in cartons, with the appropriate quantity specific to the planned dispensing schedule of the IP.

Placebo for all cohorts is 0.9% sodium chloride (sterile saline).

When prepared for dosing according to instructions, it will not be possible to distinguish between LY3316531 and placebo.

Detailed instructions for the preparation and handling of LY3316531 will be provided by the sponsor.

The IP must be prepared by an unblinded pharmacist who is not involved in any other study-related procedures.

## **7.2. Method of Treatment Assignment**

Randomization tables for allocation of LY3316531 or placebo will be prepared by the statistician or designee for the study and provided to the site pharmacists involved in dose preparation.

The allocation and dispensation of the IP will be fully documented and verified by a second person. Detailed records of the amounts of the IP received, dispensed, and remained at the end of the study will be maintained by the site pharmacy.

### **7.2.1. Selection and Timing of Doses**

The doses will be administered at approximately the same times on each day. The actual time of all dose administrations will be recorded in the patient's/subject's electronic case report form (eCRF).

## **7.3. Blinding**

Parts A and B of Study FFAA are subject- and investigator-blind except for the non-sentinel subjects and the open-label SC administration cohort in Part A (Cohort 5). Part C of Study FFAA is open-label. As a result, all patients with psoriasis who enter the study will receive LY3316531.

Pharmacy staff who prepare and dispense study medication are required to be unblinded to treatment allocation.

Subject treatment assignments and drug accountability records will be held in a secure location accessible only by individuals involved with study drug preparation or dispensation.

Blinding will be maintained throughout the conduct of the study as described in the separate Blinding Plan.

If a subject's study treatment assignment is unblinded, the subject must be discontinued from the study, unless the investigator obtains specific approval from a Lilly clinical pharmacologist or clinical research physician (CRP) for the study participant to continue in the study.

In case of an emergency, the investigator has the sole responsibility for determining if unblinding of a subject's treatment assignment is warranted for medical management of the event. The subject's safety must always be the first consideration in making such a determination. At the discretion of the investigator, if a subject's treatment assignment is unblinded, as judged by the investigator, Lilly must be notified immediately. It is the responsibility of the investigator to document the decision and rationale, promptly.

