## 8. Discontinuation Criteria

Patients/subjects discontinuing from the study prematurely for any reason must complete AE and follow-up procedures per Section 2 of this protocol.

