### 8.2. Discontinuation from the Study

Patients/subjects will be discontinued under the following circumstances:

- Enrollment in any other clinical study involving an IP or enrollment in any other type of medical research judged not to be scientifically or medically compatible with this study
- Participation in the study needs to be stopped for medical, safety, regulatory, or other reasons consistent with applicable laws, regulations, and good clinical practice (GCP)
- Investigator Decision
  - the investigator decides that the patient/subject should be discontinued from the study

- if the patient/subject, for any reason, requires treatment with another therapeutic agent that has been demonstrated to be effective for treatment of the study indication, discontinuation from the study occurs prior to introduction of the new agent
- Subject Decision
  - the patient/subject, or legal representative, requests to be withdrawn from the study.
- Sponsor Decision
  - Lilly stops the study or stops the subject's participation in the study for medical, safety, regulatory, or other reasons consistent with applicable laws, regulations, and GCP
- Suicidal Ideation and/or Behavior
  - When a subject discontinues from a study due to suicidal ideation and/or behavior, the same follow-up procedures can be used as would be done for discontinuation due to any other AEs leading to discontinuation. It is not necessary to collect additional information (except what is already requested on the C-SSRS, the Self-Harm Supplement Form, and the Self-Harm Follow-up Form).
  - Investigators are responsible for monitoring the safety of patients/subjects who have entered this study and for alerting Lilly or its designee to any event that seems unusual, even if this event may be considered an unanticipated benefit to the patient/subject.
  - The investigator is responsible for the appropriate medical care of patients/subjects during the study.
  - The investigator remains responsible for following, through an appropriate health care option, AEs that are serious or that caused the patient/subject to discontinue before completing the study. The patient/subject should be followed up until the event is resolved or explained. Frequency of follow-up evaluation is left to the discretion of the investigator
- Adverse event

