### **9.2.1. Serious Adverse Events**

An SAE is any AE from this study that results in 1 of the following:

- death
- initial or prolonged inpatient hospitalization
- a life-threatening experience (that is, immediate risk of dying)
- persistent or significant disability/incapacity
- congenital anomaly/birth defect
- important medical events that may not be immediately life-threatening or result in death or hospitalization but may jeopardize the patient or may require intervention to prevent 1 of the other outcomes listed in the definition above
- when a condition related to the injection syringe or IV drug delivery system necessitates medical or surgical intervention to preclude either permanent impairment of a body function or permanent damage to a body structure, the serious outcome of "required intervention" will be assigned.

Study site personnel must alert the Lilly CRP/clinical pharmacologist, or its designee, of any SAE as soon as practically possible.

Additionally, study site personnel must alert Lilly Global Patient Safety, or its designee, of any SAE within 24 hours of investigator awareness of the event via a sponsor-approved method. If alerts are issued via telephone, they are to be immediately followed with official notification on study-specific SAE forms. This 24-hour notification requirement refers to the initial SAE information and all follow-up SAE information.

Although all AEs are recorded in the electronic data entry/designated data transmission methods after signing informed consent, SAE reporting to the sponsor begins after the patient/subject has signed informed consent and has received IP. However, if an SAE occurs after signing informed consent, but prior to receiving IP, AND is considered Reasonably Possibly Related to a study procedure then it MUST be reported.

Investigators are not obligated to actively seek AEs or SAEs in subjects once they have discontinued from and/or completed the study (the patient/subject summary eCRF has been completed). However, if the investigator learns of any SAE, including a death, at any time after a subject has been discharged from the study, and he/she considers the event reasonably possibly related to the study treatment or study participation, the investigator must promptly notify Lilly.

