## 10. Statistical Considerations and Data Analysis

### 10.1. Sample Size Determination

The sample size for each cohort is customary for the first-in-human study in which formal power analyses is not necessary to address the objectives associated with safety, tolerability, PK, and/or PD assessments. Approximately 86 patients/subjects are planned for enrollment; however, up to 102 subjects may be enrolled to allow for replacement of subjects and any additional dose cohorts (Parts A, B, and C).

Subjects/patients who withdraw from the study before completing the Day 57 (Part A) or Day 85 (Parts B and C) assessment may be replaced if necessary to have the planned number of subjects/patients complete a dose cohort. A replacement subject/patient will be assigned the same treatment as the subject/patient he or she replaces (Parts A, B, and C).

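### After a code break the default is exit from the study, so scheduled follow-up stops after one early-discontinuation visit, even in Part A where the only dose has normally been given

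*Protocol*

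**What the plan says.** **Code break.** Protocol 7.3 gives the investigator sole responsibility for emergency unblinding. The consequence is "If a subject's study treatment assignment is unblinded, the subject must be discontinued from the study". The same sentence has an exception: "unless the investigator obtains specific approval from a Lilly clinical pharmacologist or clinical research physician (CRP"). So the default is to leave the study, and staying needs permission.

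**Follow-up after exit.** Protocol 8 says: "Patients/subjects discontinuing from the study prematurely for any reason must complete AE and follow-up procedures per Section 2 of this protocol". For AEs that are serious or led to discontinuation, 8.2 adds: "The patient/subject should be followed up until the event is resolved or explained". Section 9.2 extends this to medically important and related AEs. Against that, 9.2.1 states: "Investigators are not obligated to actively seek AEs or SAEs in subjects once they have discontinued from and/or completed the study". The Part A and Part B schedules (2.1, 2.2) give a discontinuing subject a single ED column.

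**Replacement.** Under 10.1, subjects who withdraw before Day 57 (Part A) or Day 85 (Parts B and C) "may be replaced if necessary to have the planned number of subjects/patients complete a dose cohort". It continues: "A replacement subject/patient will be assigned the same treatment as the subject/patient he or she replaces". SAP 7 repeats both statements. Protocol 5.2.2 has a different rule for Part B. Dropouts before the third dose are replaced, but safety withdrawals are not, apart from an exception when more than half of a cohort has dropped out after the third dose.

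**The concern.** Leaving treatment and leaving the study are different things, and 7.3 ties a code break to the second. In Part A the one dose has normally been given, so leaving the study takes away data and nothing else. In Part B the rule merges two decisions: whether to give further doses and whether to keep observing.

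The loss is not random. Codes are broken for the medical management of emergencies, so scheduled observation is cut short in the subjects whose later course matters most. The primary endpoint (Table FFAA.4.1) is the incidence of all AEs, TEAEs and SAEs, not only of the event that led to the code break. SAP 9.5.1 reports counts and percentages of subjects and makes no allowance for time observed. A subject who leaves on Day 2 therefore stays in the denominator as if followed to Day 85.

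The second issue is concealment. If a subject whose code was broken is replaced on the same treatment, an investigator who can tell who replaces whom can infer the assignment. That investigator judges relatedness and takes part in the escalation review as the blinded party (7.4.2).

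**Working it through.** **1. The plan's enrolment figures (10.1, Table FFAA.5.1, 5.2).**
- Planned: Part A 4+4+8+8+6+8+8 = 46; Part B 8+8 = 16; Part C 8+8+8 = 24; total 86, as stated.
- Maximum: 52+20+30 = 102, as stated.
- Room for replacements: 6 + 4 + 6 = 16. Nothing below changes these figures.

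**2. Scheduled time lost in Part A without approval to stay.** Dosing is on Day 1 and the last visit on Day 85, giving 85 − 1 = 84 postdose days. Loss = 85 − day of exit:
- Day 2: 83 days (83/84 = 99%)
- Day 15: 70 days
- Day 29: 56 days

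For an IV subject leaving on Day 2, the outpatient visits on Days 4, 8, 15, 22, 29, 43, 57, 71 and 85 (nine) are replaced by one ED visit. By APP.6.1, this loses nine PK samples, four ECG time points (Days 8, 15, 43, 85) and three ADA samples (Days 15, 29, 85), against one of each at ED. In Part B, exit on Day 58, after the third and last dose, loses 141 − 58 = 83 days.

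**3. Drug still present.** Protocol 5.4 anticipates a half-life of 2 to 3 weeks. Assuming simple exponential decay, the fraction remaining is 0.5^(days since dose / half-life):
- Day 2: 0.5^(1/14) = 95% to 0.5^(1/21) = 97%
- Day 15: 0.5^(14/14) = 50% to 0.5^(14/21) = 63%

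So observation stops while exposure continues.

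**4. Which follow-up survives exit.**
- Kept: the triggering event, to resolution or explanation (8.2, 9.2); extra PK and ADA samples for hypersensitivity reactions and, for subjects TE-ADA positive at ED, sampling about every 3 months for up to 1 year (9.6.2, APP.6.1); related SAEs that the investigator happens to learn of (9.2.1).
- Ended by default: the remaining scheduled visits and the active search for new AEs and SAEs. ADA that first appears after the ED visit is missed.

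Section 8 refers back to Section 2, which offers only the ED column, so it does not restore the schedule.

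**5. Detection, by illustration.** For events arising after exit, a cohort with 6 active subjects has 5 under observation. The chance of seeing at least one event is 1 − (1 − p)^n. The rates p are assumed; the documents give none.

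| p | n = 6 | n = 5 |
|---|---|---|
| 5% | 26.5% | 22.6% |
| 10% | 46.9% | 41.0% |
| 20% | 73.8% | 67.2% |

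In Cohorts 3, 4, 6 and 7, 7.4.2 needs Day 15 data from only 7 of 8 subjects. The subject who left can be the eighth, represented only by the data available up to exit.

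**6. Reach of the replacement inference.** Investigator-blind positions in Part A are Cohorts 3, 4, 6 and 7 (4 × 8 = 32) plus two sentinels in each of Cohorts 1 and 2 (4), making 36. Part B has 16. The total is 52 of 86 (60%). In a 6:2 cohort the investigator's prior for active drug is 6/8 = 75%. For a recognised replacement it becomes 100% or 0%. A known-placebo replacement would be 1 of 1+1+2+2+2+2 = 10 pooled placebo subjects in Part A, or 1 of at most 4 in Part B (SAP 6 pools placebo within each part).

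**The case against.** A reader might infer that an unblinded subject must always leave, that follow-up of the most important events is lost, and that every replacement is effectively unblinded. The documents do not support any of the three in that form.

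- **Leaving is not absolute.** The sentence in 7.3 contains the approval route, and the sponsor must be told of a code break immediately, so the contact needed for approval already exists. This stands. It softens the default without reversing it.
- **The triggering event is not lost.** Sections 8, 8.2, 9.2 and 9.6.2 keep it under follow-up, and safety analyses include all enrolled subjects (10.3, SAP 8), so it counts in the primary endpoint. This stands. What ends is the routine schedule and the active search for new events.
- **Replacement is limited.** It is optional in 10.1 and, for Part A, linked in 5.1.1 to missing PK data up to Day 57. Part B safety withdrawals are generally not replaced (5.2.2). One related SAE or clinically significant event stops dosing at that level (7.4.2). This largely stands, with two gaps. The single-event scenario requires an event related to LY3316531, so on its wording it would not apply if the code break showed placebo, though other scenarios might. And 5.2.2 does not say whether exit because of a code break counts as a safety withdrawal.
- **The inference needs knowledge of who replaces whom.** Randomization tables go to pharmacists (7.2), assignment records are restricted (7.3), and a separate Blinding Plan, not supplied, may deal with this. This stands, so the point is secondary.

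**Conclusion.** The point holds for scheduled observation. By default, 7.3 ends routine safety, ECG, PK, CGRP and ADA collection and the active search for new events after one ED visit. It does so selectively, in subjects with emergencies, and in Part A without any reduction in exposure once the dose has been given. The largest loss is 83 of 84 postdose days, which assumes a code break on Day 2 and no approval to stay. Later code breaks cost less, and with approval or without code breaks the effect is zero. The documents give no expected number of code breaks.

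The replacement issue is a possibility, not a demonstrated breach. It is confined to the 52 investigator-blind positions. It needs a replacement to be dosed, an investigator who broke the code and can identify that replacement, and a Blinding Plan that does not already prevent this.

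**What to change.** - **Protocol 7.3:** make continued participation in all remaining scheduled safety, PK and ADA visits the default after unblinding. Treat any decision on further Part B doses as a separate matter, on which this point takes no position. Record and list every code break. Reconcile the wording with 8, 8.2 and 9.2.1, so that it is clear which observations continue after a code break.
- **Protocol 10.1 and SAP 7:** state that unblinding alone is not a reason for replacement, and reconcile this with 5.2.2, including whether exit after a code break counts as a safety withdrawal.
- **Concealment:** state that the link between a replacement and the subject replaced is withheld from the investigator, or refer to the Blinding Plan if it already says so.

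Drawing the replacement from a separate randomisation list is not recommended. If an active subject were replaced by placebo, a 6:2 cohort would complete as 5:3, and a 7-subject review set could hold only 4 active subjects, against the 5 or 6 on which 5.1 relies. Same-treatment replacement avoids that.

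The cost is a few sentences in two documents and some further visits for a subject whose treatment is known. The planned numbers, 86 and up to 102, do not change.
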